Protocol for Almond Butter and Fasting Glucose Study

Identifiers: NCT03826472

Unique Protocol ID: PKE AlmondButter

Brief Title: Almond Butter and Fasting Glucose

Updated May 2, 2022

Protocol for Almond Butter and Fasting Glucose Study

Inclusion Criteria

- Individuals 18 to 75 years of age
- Individuals with diagnosed type 2 diabetes
- HgbA1c: <9%
- Not on insulin therapy
- On stable doses of oral antihyperglycemic agent (no dose change for 6 months) or no oral antihyperglycemic agents
- Willing and able to adhere to study protocol

Exclusion Criteria

- Individuals with type 1 diabetes, cardiovascular disease, kidney disease, liver disease, cancer or inflammatory conditions (e.g. GI disorders, rheumatoid arthritis)
- Women who are pregnant, breastfeeding, or have been pregnant within the last 6 months or breastfeeding within the last 6 weeks
- Individuals who smoke or use tobacco products
- Use of insulin therapy or sulfonylurea medications
- Almond allergy
- Allergy to Dexcom CGM adhesive

Recruitment

Advertisements will be placed in campus buildings and facilities as well as the surrounding area (gyms, churches, supermarkets, coffee shops etc.) to identify potential subjects residing in and around the State College area. We will also provide flyers to local physician offices and recruit through our Facebook page and department website.

Study staff will contact those individuals who have responded to ads (email, newspaper, website, fliers) and have left their name and phone numbers on the recruiting line or email.

Recruitment flyers will be posted in local physician offices. Cardstock fliers may also be distributed to patients or displayed in the waiting room of the office. Websites (<http://clinicaltrials.gov/>, <https://studyfinder.psu.edu/>, Facebook, Craig's List), PSU listserv (Health and Human Development Dept listserv; Food Science listserv; post-doc etc.) will also be utilized. Participants will be asked to complete a brief phone screening to confirm eligibility.

Consent Process and Documentation

Once interested participants have contacted study staff and have undergone a phone screening, an appointment will be set at the General Clinical Research

Center (GCRC) where study staff will review the consent documents with participants. At this appointment, before any procedures take place, potential participants will be given the informed consent document. Following standard protocol procedure, a trained staff person will review the information in detail, make sure the individual understands the study and answers any questions they may have. If the participant is still interested in enrolling in the study, both the participant and the staff member will sign and date the document. A copy of the signed document will be provided to the participant prior to leaving the screening appointment. If consent is obtained, the study protocol will be reviewed, the Dexcom monitor will be placed, and the subject will begin the study that day. Subjects will be made aware that their participation in this study is voluntary, they may drop out of the study at any time, and that there is no penalty for not participating. Consent will be confirmed in writing.

Protocol

After completion of the phone screening, an appointment will be set for a baseline visit at the GCRC to obtain informed consent and place the continuous glucose monitor. If the participant consents to the research, the researcher will play a brief video detailing how to use place a Dexcom Continuous Glucose Monitor (CGM), and participants will then place the monitor on themselves, under the supervision of study staff. Participants will be taught to use the CGM properly and will wear it for 3-7 days. The CGM can be worn for up to 7 days, according to manufacturers' instruction, but in some individuals, the adhesive does not stay in place for the full week. We will plan for study participants to wear the CGM for 7 days, but we will accept a minimum of 3 days of data.

The Continuous Glucose Monitor data receiver will be set to blinded mode and participants will not be able to see their glucose data for the duration of participation (they will still monitor their blood glucose as instructed by their physician, they just will not be able to see it on the CGM). Participants will wear the CGM for 3-7 days, return to the clinic for removal and replacement, and then begin the second study period. They will also be provided with the study food, almond butter, and be asked to consume the almond butter that we provide to them as a bedtime snack for the 3-7 nights of the study. The order of their treatment (control then almond butter or almond butter then control) will be randomly assigned. We will also ask participants to keep a record of what they eat for dinner, what time they eat breakfast, lunch and snacks, and any changes in medication or physical activity on those days. Participants will receive individual packets of 2 tbsp of natural almond butter and be given instructions to eat the almond butter as an evening snack, or to eat nothing after dinner during the no-snack control period. Blood glucose levels will be measured using continuous glucose monitoring (CGM), which will be provided free of charge to participants through a donation from Dexcom. At Visit 3, participants will have the CGM removed and will receive a printout of their CGM data when they return the Dexcom equipment to the office.

Visit 1

The study will be explained, questions will be answered and consent forms will be reviewed and signed. Participants providing consent will watch a brief video on use and placement of CGM, and then place their CGM in the office, supervised by study staff. They will be taught to use the CGM, be provided with the study food, food record sheets and randomized. They will also have an appointment set for 6-14 days later.

Visit 2

At the second visit, participants will remove and replace their CGM monitor. They will be reminded of all data entry requests.

Visit 3

At the third visit, participants will return their CGM equipment and their data will be downloaded. They will receive their CGM data and be entered into a drawing to win a gift card for their participation. They will receive the \$100 incentive for participation approximately two weeks later.

Duration of Participation

Participants will first complete a phone screening. If they are deemed eligible, they will participate in the study for 2 weeks, including 3 visits to the clinic. Visit 1 lasts approximately 1 hour, visits 2 and 3 last approximately 15 minutes.

Intervention Food (Almond Butter)

The almond butter will be packaged into 7 single serving containers to be consumed during the intervention week. Participants will be given individual containers as dictated by the study design, 1 per day, for the duration of the intervention, at their first visit. There are no special requirements for storage by the participants.

Subject Numbers and Statistical Plan

Ten participants were recruited for this study. All data collected, including CGM and dietary data, will be identified with a code. None of the collected data will include patient identifiers. Only the PI and study personnel will have access to study data. Linear mixed effect models in R statistical software (The R Project for Statistical Computing) will be used to analyze the data.

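### Does the lack of a rule for the Visit 2 morning put the fasting glucose contrast at risk?

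*Combined protocol and SAP*

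**What the plan says.** The title, "Protocol for Almond Butter and Fasting Glucose Study", names the only outcome the document identifies. Under Consent Process and Documentation, a consenting participant starts the study on the day the sensor is placed. In the Protocol section the two conditions are both applied in the evening: almond butter is eaten "as a bedtime snack for the 3-7 nights of the study", or participants are told "to eat nothing after dinner during the no-snack control period". Order is randomised. Between conditions, participants "return to the clinic for removal and replacement, and then begin the second study period". On wear time, the plan is for participants to "wear the CGM for 7 days, but we will accept a minimum of 3 days of data". At Visit 3, "participants will return their CGM equipment and their data will be downloaded"; no other download is described.

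The analysis is covered by one sentence under Subject Numbers and Statistical Plan, which names "Linear mixed effect models in R statistical software". It gives no definition of a fasting value and no rule linking a morning, a date or a reading to a condition. It does not say that the record will be divided by calendar date.

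**The concern.** With a daytime Visit 2, one calendar date belongs to both conditions. The fasting reading that morning follows the last night of the first condition, and the second condition starts only that evening. Since the data are downloaded at Visit 3, readings are sorted into conditions afterwards, with no written rule.

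A split that gave the whole Visit 2 date to the second period would put one wrongly labelled morning per participant into the analysis. Randomised order would not cancel the error, because the estimate is pulled toward zero in both sequences. With ten participants and possibly as few as 3 mornings per period, one morning is a sizeable share of the data.

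A related point is that the 3-day minimum is not defined as dates, 24-hour spans or fasting mornings. The placement date has no on-study fasting morning, so three dates would give 2 mornings and 72 hours would give 3.

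**Working it through.** The document states no effect size, standard deviation or power, so there is no figure of its own to reproduce. The check is a count of mornings.

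**Inputs.** From the Protocol section: 3 to 7 nights per condition, conditions applied in the evening, second period starting after the sensor change. From Consent Process and Documentation: study start on the Visit 1 day. Assumed: one fasting value per morning, equal weights, no carryover, no missing mornings, Visit 2 after the fasting reading, and the first sensor still recording that morning.

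**Layout.** Call Visit 1 day 0, Visit 2 day n1 and Visit 3 day n1 + n2. Mornings 1 to n1 follow the first condition. Mornings n1 + 1 to n1 + n2 follow the second.

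**Effect of each way of treating the Visit 2 date on the fasting contrast**

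1. *Split at the sensor change, or assign each morning to the evening before it.* The Visit 2 morning goes to the first condition. No morning is mislabelled: 0% at every n from 3 to 7.
2. *Whole date to the first condition.* The fasting mornings fall as in item 1: 0%.
3. *Date left out.* 0%, with some loss of precision. Let r be the person-by-period variance divided by the morning-to-morning variance (assumed range 0 to 1), with d nights in each period. The standard error is multiplied by sqrt((2r + 1/(d−1) + 1/d) / (2r + 2/d)), which is 1.031 to 1.118 at d = 3 and 1.005 to 1.041 at d = 7.
4. *Whole date to the second condition, Visit 3 morning counted.* That label holds n2 correct mornings and 1 wrong one, so the shrinkage is 1/(n2 + 1): 1/4 = 25.0% at 3 nights, 20.0% at 4, 16.7% at 5, 14.3% at 6 and 1/8 = 12.5% at 7. It is the same in both sequences. Only the second period's length matters: 3 then 7 nights gives 12.5%, and 7 then 3 gives 25.0%.
5. *As item 4, Visit 3 morning not counted.* Now n2 − 1 correct and 1 wrong, so 1/n2: 33.3% at 3 nights and 14.3% at 7.

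**Model check.** Mixed models were fitted to simulated data with 10 participants, a random intercept, a period term and an assumed true difference of −10. Under item 4 the mean estimate was −7.53 at 3 nights and −8.65 at 7, close to the −7.5 and −8.75 expected. With the Visit 2 morning in the first condition it was −10.31 and −10.11.

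**Which of these the protocol implies.** Period 2 starts only once the sensor has been replaced. A reading taken before that visit is therefore in period 1, as in item 1. Items 4 and 5 need an analyst to place in period 2 a reading taken before period 2 began.

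**The 3-day minimum.** Having 2 mornings instead of 3 multiplies the standard error by sqrt((r + 1/2)/(r + 1/3)), which is 1.061 at r = 1 and 1.225 at r = 0. The Protocol section also gives the snack period as 3 to 7 nights, and three nights have three following mornings, so the 2-morning reading fits the text poorly.

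**The case for a change.** The strongest case for a change is that an implied boundary is not an analysis rule. The labelling conventions give results from no shrinkage to a third, the error would run the same way in every participant, the study is small, and one or two sentences would close the gap without touching any procedure.

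What stands: no rule is written, the Visit 2 date does span both conditions, and the arithmetic for the harmful convention is right.

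What does not stand is that the plan leads there. The order of events, the change of sensor and the evening timing of both conditions all point to the same assignment, and the records of breakfast and snack times help confirm it. The larger percentages are also not the typical case. Duration of Participation and Intervention Food (Almond Butter) describe two weeks and seven servings, where the harmful labelling costs 12.5% if the Visit 3 morning is counted. The Protocol section attributes shorter wear to adhesive failure; if the first sensor came off before the Visit 2 morning, there is no reading to misassign. The 25% case remains possible, for instance if only the second sensor fails early.

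A strict requirement of 3 mornings per period could exclude people from a ten-person study, although a mixed model accommodates unequal numbers of mornings.

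**Conclusion.** No change to the plan follows. The missing rule is a gap in detail, and reading the protocol in its own order fills it with the correct assignment: the Visit 2 morning belongs to the first condition and the Visit 3 morning to the second. On that reading the fasting contrast is not shrunk at all. A loss of 12.5% to 25%, or 14.3% to 33.3% without the Visit 3 morning, arises only from labelling the whole Visit 2 date as the second condition, which the protocol does not ask for and which runs against its stated sequence.

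The conclusion for a split at the sensor change assumes that Visit 2 comes after the fasting reading; the document gives no visit clock times. Assignment by the preceding evening does not need that assumption. The undefined 3-day minimum is likewise a matter of wording, and the stated number of nights largely settles it. Writing the assignment down would record what a careful analyst would do anyway and would not alter the result.

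### Does the 6–14 day appointment set at Visit 1 contradict the 3–7 day first period?

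*Combined protocol and SAP*

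**What the plan says.** The Visit 1 entry covers consent, sensor placement, supply of the food and record sheets, and randomisation. It then adds: "They will also have an appointment set for 6-14 days later". It does not say which appointment. The Visit 2 and Visit 3 entries that follow give no day or window.

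Timing is given in four other places:

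- **Protocol section, first period.** "Participants will wear the CGM for 3-7 days, return to the clinic for removal and replacement, and then begin the second study period". That return to the clinic is Visit 2.
- **Protocol section, sensor wear.** "The CGM can be worn for up to 7 days, according to manufacturers' instruction", and for data: "We will plan for study participants to wear the CGM for 7 days, but we will accept a minimum of 3 days of data". The almond butter is to be eaten "as a bedtime snack for the 3-7 nights of the study".
- **Intervention Food.** The almond butter is "packaged into 7 single serving containers to be consumed during the intervention week".
- **Duration of Participation.** Eligible people are told that "they will participate in the study for 2 weeks, including 3 visits to the clinic".

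The statistical plan names linear mixed effect models and ten recruited participants. It gives no rule for assigning nights to a condition.

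**The concern.** An appointment made at Visit 1 is naturally taken to be the next one, and the sentence sits directly above the Visit 2 entry. Read that way, the crossover falls at 6–14 days, while the Protocol section puts it at 3–7 days.

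If sites followed the longer interval, a first period could outlast the sensor. For participants given almond butter first, it could also outlast the seven containers. There would be days without glucose readings, a gap between periods that differs from person to person, and doubt about which condition applied on the uncovered days.

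Visit 2 is the date that divides almond butter readings from control readings. With ten participants, and as few as 3 days of data accepted, wrongly assigned or lost nights would be a noticeable share of the data.

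**Working it through.** **Inputs.** Period length 3–7 days, sensor limit 7 days, and two treatment orders, hence two periods (Protocol section). Seven containers (Intervention Food). Two weeks, or 14 days, and three visits (Duration of Participation). Unnamed appointment at 6–14 days (Visit 1). No washout is described: the sensor is swapped at the clinic and the second period then begins, so the periods are taken as consecutive.

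**Step 1: reproduce the 6–14 days.** Visit 1 to Visit 3 = period 1 + period 2.

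- Shortest: 3 + 3 = 6 days.
- Longest: 7 + 7 = 14 days.

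Both ends match the stated interval.

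**Step 2: test each reading against the other figures.**

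| Figure in the protocol | Appointment is Visit 3 | Appointment is Visit 2 |
|---|---|---|
| First period 3–7 days | Visit 2 stays at day 3–7, as the Protocol section says | Only days 6 and 7 agree (2 of 9) |
| Sensor limit 7 days | Each sensor worn at most 7 days | Days 8–14 (7 of 9) exceed it by 1–7 days |
| Seven containers | 3–7 nights, supply sufficient | Exceeded on days 8–14, almond-butter-first order only |
| Two weeks in total | 6–14 days | 6 + 3 = 9 to 14 + 7 = 21 days |

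The first column has no conflict. The second conflicts over most of the window but not all of it: with Visit 2 on day 6 or 7, the total is 6 + 3 = 9 to 7 + 7 = 14 days, and every figure is met. Day 7 is also the planned wear.

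**Step 3: the worst case on the Visit 2 reading.**

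- With Visit 2 on day 14, the total is 14 + 3 = 17 to 14 + 7 = 21 days.
- If a sensor fails on day 3 and is replaced only at the scheduled visit, the gap is 6 − 3 = 3 to 14 − 3 = 11 days. This assumes the participant cannot come back early. The protocol nowhere says so, and its own 3–7 day period allows a return from day 3.

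**Step 4: what reaches the analysis.** A night without a sensor yields no reading and cannot enter the model. A night with a sensor is assigned by the randomised order and the actual date of Visit 2. The mixed model accepts different numbers of nights per person, and the 3–7 day range already makes the periods unequal whatever the appointment sentence means.

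**The case for a change.** The strongest case for a change is that either reading leaves something undone. If Visit 2 is meant, the interval conflicts with the 3–7 day period. If Visit 3 is meant, the visit entries schedule the last visit and are silent on the crossover visit, the one that matters most. The statistical plan does not fill the gap, since it names a model and has no rule for including nights. Clarifying the text would need no extra visits, equipment or participants.

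Part of this stands. The sentence does not name its visit, its position invites misreading, and no rule for counting nights is written down.

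The rest does not. The crossover visit does have a window: the Protocol section gives it, and the Visit 2 entry merely does not repeat it. Nor is it true that the two statements cannot both be followed. Under the Visit 3 reading they agree throughout, and under the Visit 2 reading they agree on days 6 and 7. The unwritten night rule is one that analysts apply as a matter of course. Finally, the protocol reports recruitment of the ten participants in the past tense, so a wording edit may come too late to affect conduct.

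**Conclusion.** The concern does not call for a change. The sentence is ambiguous, but no contradiction is shown: 6–14 days is exactly twice 3–7 days, ends at the stated two weeks, and fits the sensor limit and the snack supply when read as the final visit. On that reading the number of uncovered days is zero and no result changes. No sample size, power or error-rate figure is involved.

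This rests on three assumptions: the two periods run consecutively; actual visit dates are available to the analyst; and Visit 2 took place at 3–7 days, as the Protocol section sets out. Nothing in the documents indicates that crossover visits were held on days 8–14. Had they been, up to 7 days per participant would lack a sensor. The analyst would see this in the dates and would leave those days out.

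### Must CGM data be checked against the 3-day minimum before crossover, with a rule for a short period?

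*Combined protocol and SAP*

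**What the plan says.** The Protocol section of the combined document sets the wear target and the floor: "We will plan for study participants to wear the CGM for 7 days, but we will accept a minimum of 3 days of data". It gives early adhesive failure as the reason for the range. It does not say whether the floor applies to each period or what counts as a day.

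The same section has participants "return to the clinic for removal and replacement, and then begin the second study period", with no condition on the period-1 data. Under Visit 2 the listed tasks are the swap ("At the second visit, participants will remove and replace their CGM monitor") and a reminder about data entry. Under Visit 3: "At the third visit, participants will return their CGM equipment and their data will be downloaded". That is also when participants "will receive a printout of their CGM data when they return the Dexcom equipment to the office". The receiver is blinded to participants; staff access is not restricted.

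Subject Numbers and Statistical Plan states "Ten participants were recruited for this study" and names linear mixed effect models in R. It gives no model terms and no handling of short or missing periods.

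**The concern.** A minimum is set, but no step verifies it and no consequence is attached. Followed literally, the schedule would reveal a short first period only after the condition had changed, and a short second period only at the visit where the participant leaves and receives the printout. By then the same condition can no longer be completed within the stated visits.

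The treatment effect rests on at most ten within-person differences, so each one counts. A mixed model does not rescue a participant who has only one period, because that person contributes almost nothing to the within-person contrast. A count of days at visits that take place anyway looks like inexpensive protection.

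**Working it through.** The plan has no sample-size calculation or precision figure to reproduce. The calculations below size the gap. The shortfall rates, correlations and variance ratio are assumptions; the documents give none of them.

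**1. Cost of losing a whole pair.** The 95% CI half-width for a mean paired difference, in units of the SD of the differences, is t(0.975, n−1)/√n.

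| Complete pairs | Half-width (SD) | Change from row above |
|---|---|---|
| 10 | 0.715 | |
| 9 | 0.769 | +7.5% |
| 8 | 0.836 | +8.8% |

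**2. What one period is worth.** Take a model with fixed treatment and period and a random participant intercept. Compare the information on treatment from nine pairs plus one single-period participant with that from nine and from ten pairs. The single-period participant keeps 25%, 15% or 5% of a full pair's information at within-person correlation 0.5, 0.7 or 0.9. So an empty period is a real loss.

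**3. How many pairs are at risk.** Let s be the chance that a sensor gives under 3 days without anyone noticing, independent across sensors, with any repeat failing at the same rate. Expected complete pairs out of 10 are 10(1−s)² with no check, 10(1−s²)(1−s) with a Visit 2 check only, and 10(1−s²)² with checks and one repeat in both periods. Averaging the half-width over the binomial number of complete pairs gives the expected widening.

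| s (assumed) | Pairs, no check | Pairs, Visit 2 check | Pairs, both checks | Expected half-width, none vs both | Widening |
|---|---|---|---|---|---|
| 1% | 9.80 | 9.90 | 10.00 | 0.726 vs 0.715 | 1.5% |
| 2% | 9.60 | 9.80 | 9.99 | 0.738 vs 0.716 | 3.0% |
| 5% | 9.03 | 9.48 | 9.95 | 0.774 vs 0.718 | 7.8% |

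The 7.5% step in the first table applies only once a whole pair has gone. At 1% or 2% the expected effect is well below it.

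**4. A short period is not an empty one.** Fewer than 3 days includes 1 or 2 days. If nightly values are modelled (an assumption), the variance of a participant's treatment difference is 2τ² + σ²(1/a + 1/b). Here a and b are the nights in each period, σ² is the nightly variance and τ² is the person-by-period variance. Information relative to 7 against 7 nights:

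- τ² = 0, 7 against 2 nights: (2/7)/(1/7 + 1/2) = 0.286/0.643 = 44%.
- τ² = 0, 7 against 1 night: 0.286/1.143 = 25%.
- τ² = 0.3σ², 7 against 2: (0.6 + 0.286)/(0.6 + 0.643) = 71%.
- τ² = 0.3σ², 7 against 1: 0.886/1.743 = 51%.

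The first two are floors, because any person-by-period variance raises the share kept. Step 3 counts every shortfall as a lost pair, so its losses are upper bounds, reached only if short periods are excluded or empty.

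**The case for a change.** The best argument for acting is that both omissions are real and that writing down a check is cheap. Visits 2 and 3 already take place, and counting days need not reveal glucose values. If staff check anyway, stating it makes handling uniform. Participants cannot see their readings, so signal loss or partial recording could pass unnoticed, and no instruction to report a detached sensor is given. At the assumed rates, the chance that at least one of the 20 sensor periods falls short is 1−(1−s)²⁰, or 18%, 33% and 64%. Deciding what to do with a short period after seeing its data would also be a post hoc choice.

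The omissions stand, and so does the point about post hoc choice. The case for new visit procedures is weaker. The rates have no source in the documents, and the adhesive failure they do mention is ordinarily visible. The count takes minutes, but acting on it does not: an affected participant may need another sensor, days beyond the planned two weeks, a fourth visit, and more almond butter than the single week's supply described ("The almond butter will be packaged into 7 single serving containers to be consumed during the intervention week"). A Visit 2 check alone removes only about half the expected loss, so the procedure would have to cover both periods. Finally, recruitment is reported in the past tense in a version updated on May 2, 2022. That does not prove data collection has closed, but it makes new visit steps doubtful.

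**Conclusion.** No change to the plan is needed. The minimum has no stated check and no stated consequence, but this is missing detail in a very short protocol, not a plan to proceed regardless of the data. Nothing in the text prevents staff from examining the receiver at Visit 2.

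Followed as written, the randomised within-person comparison remains valid, provided shortfalls are unrelated to glucose. The cost is precision: an expected widening of roughly 1.5% to 3% at assumed unnoticed-shortfall rates of 1% to 2%, and up to 7.8% at 5%. It is less if some shortfalls are noticed anyway or if short periods contribute their available nights.

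The remaining question is whether the floor applies per period, and whether a period below it is dropped or used as it stands. A competent analyst settles this before fitting the mixed model and reports days of data by participant and period. The conclusion would be weaker if silent sensor failure were common in this setting, which the documents neither show nor suggest.

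### All seven almond butter servings are handed out at Visit 1 in either sequence, with no return or count, so control-first participants hold the study snack through their no-snack period.

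*Combined protocol and SAP*

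**What the plan says.** Under Intervention Food (Almond Butter): "The almond butter will be packaged into 7 single serving containers to be consumed during the intervention week". The next sentence has the containers handed over "1 per day, for the duration of the intervention, at their first visit". The Visit 1 list agrees: consenting participants are to "be provided with the study food, food record sheets and randomized". Neither place makes an exception by sequence.

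The Protocol section randomises the order, so some participants start with control. In that period they are to "eat nothing after dinner during the no-snack control period". The second period opens at the second clinic visit: "Participants will wear the CGM for 3-7 days, return to the clinic for removal and replacement, and then begin the second study period".

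The later visits are listed briefly. The list for Visit 2 reads "At the second visit, participants will remove and replace their CGM monitor" and then adds a reminder: "They will be reminded of all data entry requests". The list for the last visit, Visit 3, opens with "At the third visit, participants will return their CGM equipment and their data will be downloaded", followed by feedback of the data and the participation incentives. Neither list mentions supply, return or count of almond butter.

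**The concern.** The control condition consists of not eating in the evening. For half the design, the plan puts the full set of study snacks in the participant's home before that condition starts, although none is due until it ends. The plan then has no physical check on when, or whether, the servings were used. The only related record is the participant's own. It covers what was eaten at dinner and the times of breakfast, lunch and snacks, so it gives the time of a snack but not its content.

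What is at stake is the size of the contrast. If a study serving has the same effect on a control night as on an almond night, eating one early makes the control period look more like the almond period. Because 7 containers match 7 planned nights and no resupply is listed, it may also leave one almond night without a serving. With ten participants, each person's difference is about a tenth of the estimate.

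**Working it through.** The plan gives no figure to reproduce. The check is a comparison of sections, then one illustration.

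**Who holds servings during control**

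- Control-first: 7 servings supplied at Visit 1 and none due before Visit 2, so all 7 are at home through the whole control period.
- Almond-butter-first: 7 supplied, 7 eaten over the planned 7 nights, 7 − 7 = 0 carried into control. Some could be left if the almond period is cut short, but the documents do not fix how many.

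Two phrases might point the other way. The supply sentence says that containers are given in line with the study design, which could hint at supply by sequence; but the same sentence ends by naming the first visit. The Protocol section mentions provision of the food just after describing the start of the second period, but ties it to no visit.

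**Illustration of size**

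Inputs from the documents: 7 servings, 7 planned nights per period, 10 participants. Assumptions: a 5:5 split between sequences (no allocation ratio is given); a serving has effect 1 on the night it is eaten and 0 on other nights; one lapse means one study serving eaten on one control night. No lapse rate is given, so these are scenarios and not estimates.

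*Every control-first participant lapses once.* The control mean is then 1/7.

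- Serving replaced: the almond mean is 7/7, so the control-first difference is 7/7 − 1/7 = 6/7. Averaged with the undisturbed sequence: (6/7 + 1)/2 = 13/14 = 93%.
- Serving not replaced: the almond mean is 6/7, so the difference is 6/7 − 1/7 = 5/7. Averaged: (5/7 + 1)/2 = 12/14 = 86%.

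*One lapse in the whole trial.* One person in ten is affected.

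- Replaced: loss 1/10 × 1/7 = 1/70 = 1.4%.
- Not replaced: loss 1/10 × 2/7 = 2/70 = 2.9%.

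*Dependence on the split, when every control-first participant lapses.* With a period term in the model, the two sequence means are averaged equally and 93% and 86% hold at any split. The plan names linear mixed effect models but states no terms. Without a period term:

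- 7 of 10 control-first: 0.7 × 6/7 + 0.3 = 90% (replaced) and 0.7 × 5/7 + 0.3 = 80% (not replaced).
- 3 of 10 control-first: 0.3 × 6/7 + 0.7 = 96% and 0.3 × 5/7 + 0.7 = 91%.

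**The case against.** The strongest reply is that this is an opportunity and not a demonstrated fault. Participants are told plainly not to eat after dinner in control, and withholding seven packets does not enforce that rule at home, where other food is always available. Handing out a food with no special storage needs at one visit is a workable choice. All of this stands, and it is why the point is small. It does not remove the point, because supply at an existing visit would take away one avoidable source at almost no cost.

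Second, the 86% needs two things at once: a lapse by every control-first participant, and no replacement serving. No resupply is listed, but none is barred, and these participants attend Visit 2 just before their almond period. That also stands, so 93% and 86% must be read together, next to the single-lapse loss of at most about 3%.

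Third, the Subject Numbers and Statistical Plan section reports recruitment of ten participants in the past tense, in a document updated in May 2022. Supply may be over. The documents do not settle this, since the procedures are written in the future tense, so the fix has to cover both cases.

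A reader might also infer that a lapse can only shrink the contrast and could never create a false benefit. The documents do not support that. It follows only if a study serving on a control night acts like a bedtime serving. One eaten overnight or shortly before a morning reading could raise control glucose instead, and the plan fixes neither the clock time of the snack nor the glucose window. Dilution is the likely direction, not a certain one.

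**Conclusion.** The point holds as a cheap improvement of the lowest severity. As written, supply takes place at Visit 1 whatever the order, control-first participants hold the study food through control, and no container is returned or counted.

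The likely effect is some dilution of the contrast. Its size cannot be estimated from the documents. The scenarios run from a loss of 1.4% to 2.9% for one lapse in the trial to a loss of about 7% to 14% if every control-first participant lapses once. They assume 7 nights per period, a 5:5 split and a serving effect confined to its own night.

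Three further inferences are not supported. Nothing shows that any participant ate the snack during control. The accepted minimum of 3 days concerns usable CGM data, so it does not establish how many servings were eaten or left over; the illustration therefore stays at the planned 7 nights. And a reanalysis that leaves out suspect nights cannot be relied on to repair the estimate: the listed record items do not identify what a snack was, a participant who breaks the rule may not record it, the plan does not say that the unit of analysis is the night, and the exclusion would rest on behaviour after randomisation.

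**What to change.** **If supply is still under way.** In Intervention Food (Almond Butter), replace the phrase that fixes supply at the first visit with: 'at the visit that opens the almond-butter period (Visit 1 for almond-butter-first, Visit 2 for control-first)'. Change the Visit 1 and Visit 2 lists to match. Add collection and count of leftover containers at the existing visit that closes the almond butter period: Visit 2 for almond-butter-first, Visit 3 for control-first. The cost is wording and a few minutes at visits already planned, with no added visit or product. The count shows how many servings were left, not when the others were eaten, and other food at home can still break the control rule.

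**If supply is finished.** State as a limitation that control-first participants held the study food during their control period and that no container count was made. The cost is one sentence. Do not rely on a refit that drops nights.
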